- · System Usability Scale (SUS)^{72,85}: The SUS is a brief, reliable and valid instrument to measure perceptions of usability of technology devices, with higher scores reflecting greater usability (maximum score of 100). We will administer the SUS for the SQC app and iCO monitor at Weeks 8, 12 and 24 follow-ups in the intervention condition only.
- · Acceptability questionnaires: Participants will complete a questionnaire developed by our team to rate the protocol from 1-10 in the following areas: perceived helpfulness, understandability, and likelihood of use at Weeks 8, 12, and 24 follow-ups in the intervention condition only. The Client Satisfaction Questionnaire-8, a validated measure of client satisfaction with behavioral interventions, will also be administered. Total mobile app data usage of iCO and SQC will be recorded and participants will be asked to record usage of iCO or SQC apps daily on the TLFB paper log (see Section 3C11).

Aim 2: Retention (Attendance)

We will record attendance at each weekly session in both conditions during the eight-week study period. For intervention participants, the study team will document attendance and duration of each visit (target 20-30 minutes). For control participants, the study team will contact participants once weekly and inquire about their participation in the QL session for that week and estimate the number of minutes in each QL session. Per VA guidelines, intervention participants will receive a reminder call the day before each weekly appointment and will receive three outreach calls after a missed appointment before the visit is considered a no-show. Rescheduled appointments must be completed within the week of the originally scheduled visit; those that are not will be considered a no-show. Patients who decide to stop treatment or stop attending treatment in both conditions will be invited to complete follow-up assessments.

Exploratory Aims: Tobacco Use and PTSD Symptoms

Use of cigarette, e-cigarette, and chewing tobacco: We will use the TLFB method to record use of nonprescribed nicotine and tobacco products for past 30 days at Week 0 (baseline) and at Weeks 8, 12, and 24.⁷¹ Seven-day and 30-day point prevalence abstinence will be assessed at 12 weeks and 24 weeks and will be defined as (1) no smoking and no use of e-

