cigarette or non-cigarette tobacco on any of the seven and 30 consecutive days prior to the assessment, respectively; and (2) salivary cotinine levels < 10 nanograms/milliliter.⁸⁶ For participants using NRT and for those who reported use of smokeless tobacco, e-cigarettes during the study, abstinence status will be independently verified by a friend or family member. Participants with missing salivary cotinine or those unable to obtain verification from a friend or family member will be considered non-abstinent. Participants will be provided with postage-paid mailers, a collection kit, and detailed instructions for saliva collection and will be asked to collect specimens, store them in their home freezer, and mail them to our lab, where they will be batch shipped on dry ice to the Salimetrics lab for analysis.

- · Nicotine dependence: We will administer the FTND at Weeks 0, 8, 12, and 24.
- PTSD symptoms: We will administer the PCL-5 at Weeks 0, 8, 12, and 24.

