6.2.1 Efficacy

Although examining efficacy is not a primary aim of the study, we will complete the following measures to preliminarily examine efficacy:

Use of cigarette, e-cigarette, and chewing tobacco: We will use the TLFB method to record use of nonprescribed nicotine and tobacco products for past 30 days at Week 0 (baseline) and at Weeks 8, 12, and 24.71 Seven-day and 30-day point prevalence abstinence will be assessed at 12 weeks and 24 weeks and will be defined as (1) no smoking and no use of e-cigarette or non-cigarette tobacco on any of the seven and 30 consecutive days prior to the assessment, respectively; and (2) salivary cotinine levels < 10 nanograms/milliliter.86 For participants using NRT and for those who reported use of smokeless tobacco, e-cigarettes during the study, abstinence status will be independently verified by a friend or family member. Participants with missing salivary cotinine or those unable to obtain verification from a friend or family member will be considered non-abstinent. Participants will be provided with postage-paid mailers, a collection kit, and detailed instructions for saliva collection and will be asked to collect specimens, store them in their home freezer, and mail them to our lab, where they will be batch shipped on dry ice to the Salimetrics lab for analysis.

Nicotine dependence: We will administer the FTND at Weeks 0, 8, 12, and 24.

PTSD symptoms: We will administer the PCL-5 at Weeks 0, 8, 12, and 24.

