6.2.4 Biomarkers (if applicable)

In the RCT, abstinence from tobacco will be bioverified with salivary cotinine levels, which is described in the study consent form (no additional consent needed). For salivary cotinine samples, participants will be provided with postage-paid mailers, a collection kit, and detailed instructions for saliva collection and will be asked to collect specimens, store in their

home freezer, and to mail to our lab, where they will be batch shipped on dry ice to the Salimetrics lab for analysis. Study personnel will be trained in biosafety procedures for handling saliva samples per VA and UCSF guidelines. Salivary cotinine specimens will be stored and batch shipped using deidentified subject identification numbers on dry ice to the Salimetrics laboratory for analysis and samples will be destroyed after completion of analysis. Results will be mailed to the research coordinator and the PI, [name], and stored in the locked cabinet and encrypted database.

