Specifically, we will conduct a 20-minute semi-structured, audio-recorded telephone interview at Week 8 with intervention condition participants only to collect in-depth feedback about user satisfaction with features of the overall intervention and its components (telephone sessions, SQC app, iCO monitor). We will use a framework of open-ended questions based on an interview guide developed by the study team, similar to that used in the focus groups with an emphasis on the acceptability of the intervention and its individual components (telephone sessions, SQC app, iCO monitor) in a therapeutic context during a quit attempt. Interviews will be audio-recorded and transcribed by a HIPAA-compliant transcription service used by our team. Audio-recordings will be uploaded and saved in the research drive on the VA server and then immediately erased from audio-recording devices.

Outline for Week 8 Qualitative Interview

- Individual features of each component of the intervention (telephone sessions, SQC app, iCO monitor)and perceived helpfulness
- Feasibility and acceptability in rural and urban settings

- Acceptability of the intervention in a military/ veteran cultural context -Anticipated barriers and facilitators of implementation
- Balance of adequate therapeutic intervention versus time burden --Scheduling issues
- Cost-effectiveness
- Mobile device accessibility and connectivity, including WiFi and battery usage

Secondary outcomes to be measured include:

(1) Self-reported cigarette, e-cigarette and smokeless tobacco use assessed by Timeline Follow-Back (TLFB)⁷⁶;(2) PTSD symptom severity assessed by PTSD Checklist-5 (PCL-5)¹⁷;(3) Nicotine dependence assessed by Fagerström Test for Nicotine Dependence (FTND)¹⁶ at Weeks 0, 8, 12, and 24; and(4) Bioverified seven and 30-day point prevalence abstinence rates assessed by self-report and confirmed with salivary cotinine levels (or independent verification by friend or family member if on NRT) at Weeks 12 and 24. (Details on the saliva collection process and use to assess point prevalence abstinence base on cotinine content of saliva are further explained in the attached documents: "Cotinine Saliva Collection" and "Oral Swab Collection Instructions".)

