6.4.5 Handling of Missing Data

Missing data can arise from several sources, including participant dropout or participant failure to complete occasional measures. For the analyses of smoking outcomes, we will conduct analyses in two ways: a complete-case approach using observed data, and to assume missing as the negative outcome (e.g., missing=non-abstinent) to obtain a range of the intervention effects. We will use the maximum likelihood approach of the mixed model to accommodate missing outcome variables without bias under the assumption of missing at random, meaning that missingness is random conditional on observed variables. This is a reasonable assumption for missing data not under the participants' control and sporadic missing items on measures.

7 - Trial Administration

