Laboratory studies will include salivary cotinine, a biomarker of recent tobacco use. Participants will collect the saliva samples themselves. Staff will instruct participants to provide a saliva sample through a straw into a cryovial. Prior to saliva collection, volunteers will rinse their mouths two times with water, and then complete saliva collection ten minutes later. Each specimen will contain 2 ml of saliva. The following amount is needed: cotinine= 75 microliters. A total of 2 ml of saliva per specimen will allow for biomarkers to be assayed in each sample.

After collection participants will store the samples in a personal cooler container provided by the study, placed in their freezer, and shipped in a prepackaged Fedex shipping package the next day. Upon receipt of the sample, research coordinator will then store the samples at -80 C and batch shipped on dry ice to the Salimetrics laboratory. They will then be analyzed at the laboratory using standard procedures. Results will be mailed to the research coordinator and the PI [name]. Only subject IDs will be used and no personal identifiers will be on the samples or the results.

Storage: Upon receipt of the specimens, the research coordinator will label the specimens with participant ID numbers (no unique identifiers), added to a tracking database, and stored at -80 Celsius in freezers at the SFVAMC for no more than 4 months. The coordinator will ship the specimens via FedEx overnight in batches on dry ice to Salimetrics laboratory for analysis. The specimens will not be stored for future use. Laboratory results will be mailed to the study coordinator, who will then manually enter results into the password-protected study database. [name], PI will also receive a copy of the lab results.

Participants will be provided with information about salivary sampling during the informed consent process and will have the opportunity to decline participation based on that information. Participants will be informed that they may withdraw consent at any time, and we will destroy any samples that have been stored. Participants are not required to follow any dietary restrictions or special instructions prior to the saliva collection.

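### The rule for verifying abstinence contradicts itself for non-NRT participants who reported e-cigarette or smokeless use, and is ambiguous for NRT users

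*Combined protocol and SAP*

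**What the plan says.** Section 6.1.3 (Exploratory Aims) introduces the outcome with "Seven-day and 30-day point prevalence abstinence will be assessed at 12 weeks and 24 weeks and will be defined as" two conditions joined by "and" in sense: self-report, and salivary cotinine below 10 ng/mL. Section 6.2.1 repeats the definition; its self-report condition is "no smoking and no use of e-cigarette or non-cigarette tobacco on any of the seven and 30 consecutive days prior to the assessment".

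Both sections then add a second verification route, through a relative or friend: "For participants using NRT and for those who reported use of smokeless tobacco, e-cigarettes during the study, abstinence status will be independently verified". They close with a failure rule: "Participants with missing salivary cotinine or those unable to obtain verification from a friend or family member will be considered non-abstinent". That rule is not limited to either route.

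Section 6.3.1, listing the secondary outcomes, says that abstinence is "confirmed with salivary cotinine levels (or independent verification by friend or family member if on NRT) at Weeks 12 and 24". It makes no exception for e-cigarette or smokeless tobacco users.

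Section 6.2.4 mentions cotinine alone: "In the RCT, abstinence from tobacco will be bioverified with salivary cotinine levels".

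Section 6.4.5 plans two analyses of smoking outcomes: "a complete-case approach using observed data, and to assume missing as the negative outcome".

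**The concern.** Anyone coding the outcome needs to know, for each participant, which evidence decides. For one group the sections name different evidence. For another they leave open whether one piece of evidence is enough or two are needed.

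The second group is likely to occur. Section 6.3.1 has NRT offered and encouraged in both arms, and Section 6.3.5 allows it to continue through Week 24, so NRT use can overlap both abstinence assessments. If a coder applied 6.1.3/6.2.1 to the letter, a truly abstinent NRT user with raised or missing cotinine would be recorded as non-abstinent. The missing-data analyses in 6.4.5 partly bracket a missing sample. They do not cover a raised one, because a raised result is observed data.

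At stake is a listed secondary outcome. Section 6.4.2 also says that the pilot will supply effect sizes for a future trial, although it does not say for which outcome.

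**Working it through.** There is no figure in the plan to reproduce. The check is to apply each section's rule to every possible result for a participant who self-reports abstinence in the window: cotinine below 10, at or above 10, or missing, crossed with contact confirms yes or no. That gives six patterns per group. A = abstinent, N = non-abstinent. The "replaces" reading also takes the missing-cotinine rule to apply only to those whose route is cotinine.

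**Not on NRT, e-cigarette or smokeless use reported during the study**

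| Cotinine | Contact confirms | 6.1.3/6.2.1, contact replaces | 6.1.3/6.2.1, contact added | 6.3.1 |
|---|---|---|---|---|
| <10 | yes | A | A | A |
| <10 | no | N | N | A |
| ≥10 | yes | A | N | N |
| ≥10 | no | N | N | N |
| missing | yes | A | N | N |
| missing | no | N | N | N |

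Against 6.3.1, the replacement reading differs in 3 of 6 patterns and the added reading in 1 of 6. Neither reading gives agreement. In practice this group consists of people whose product use fell before the abstinence window, because use inside the window already fails self-report.

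**Using NRT**

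| Cotinine | Contact confirms | 6.1.3/6.2.1, replaces | 6.1.3/6.2.1, added (literal) | 6.3.1, either suffices | 6.3.1, replaces |
|---|---|---|---|---|---|
| <10 | yes | A | A | A | A |
| <10 | no | N | N | A | N |
| ≥10 | yes | A | N | A | A |
| ≥10 | no | N | N | N | N |
| missing | yes | A | N | A | A |
| missing | no | N | N | N | N |

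If replacement is meant in all sections, 0 of 6 differ. If 6.1.3/6.2.1 are taken literally, 3 of 6 differ from an either-suffices reading of 6.3.1 and 2 of 6 from a replacement reading. If 6.1.3/6.2.1 mean replacement but 6.3.1 means that either suffices, 1 of 6 differs.

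**Neither NRT nor other products:** 0 of 6 differ.

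**Illustration only; every input is assumed.** Take 8 true abstainers in an arm of 40, a share p = 0.5 on NRT, a share f = 0.75 of those with raised or missing cotinine, and a share c = 0.7 to 1 of contacts confirming.

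- Literal 6.1.3/6.2.1: 8 × (1 − p + p(1 − f)c) = 4.7 to 5.
- 6.3.1, either suffices: 8 × (1 − p + p(1 − f) + pfc) = 7.1 to 8, a gap of 2.4 to 3.
- 6.3.1, replacement: 8 × (1 − p + pc) = 6.8 to 8, a gap of 2.1 to 3.

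With p from 0.25 to 0.75, f from 0.5 to 1 and c from 0.7 to 1, the gap against the replacement reading, 8pfc, runs from 0.7 to 6. All of these gaps need the literal reading.

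For the contradicted group, if 10% to 50% of the 4 abstainers not on NRT reported earlier product use, 4 × 0.10 = 0.4 to 4 × 0.50 = 2 per arm are verified differently. At 70% confirmation, 0.4 × 0.3 = 0.12 to 2 × 0.3 = 0.6 of them are non-abstinent under 6.1.3/6.2.1 but abstinent under 6.3.1, assuming that they return a sample below 10 ng/mL.

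**The case against.** The best reply is that the full definition appears twice in the same words, in 6.1.3 and 6.2.1, and that the parenthesis in 6.3.1 is shorthand in a schedule narrative. Section 6.3.1 also points to attachments on saliva collection that are not in the text available here. This is a fair account of how the mismatch arose, and it is a good reason to treat 6.2.4 as a summary and not as a third rule. It does not remove the mismatch: 6.3.1 states a condition for the contact route, and that condition excludes people whom 6.1.3 and 6.2.1 send there.

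A reader might infer that the sections also contradict each other for NRT users. The documents do not support that. All three sections use a friend or relative for this group, and the failure rule can be read as one failure condition per route. Replacement is the more plausible intent, and if it is meant throughout, the sections agree. What stands is that 6.1.3 and 6.2.1 do not say so.

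A reader might also infer a bias towards one arm. Any single rule would apply to both arms under 1:1 randomization, and the documents give no NRT or product-use rates by arm from which to derive a direction.

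**Conclusion.** One contradiction survives every reading: how to verify abstinence in participants not on NRT who reported e-cigarette or smokeless use during the study. It changes the classification in 3 of 6 result patterns if the contact replaces cotinine, and in 1 of 6 if it is added. For NRT users there is an ambiguity, which becomes a conflict if 6.1.3/6.2.1 are applied literally.

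The number affected cannot be derived, because the plan gives no rates of NRT, e-cigarette or smokeless use at Weeks 12 and 24. The counts above illustrate assumed inputs and are not estimates. A reader might infer that the trial's main conclusions are exposed. They are not: 6.2.1 says that efficacy is not a primary aim, and feasibility, acceptability and retention do not use this rule. Severity is low to moderate.

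**What to change.** Before outcomes are coded, put one rule in 6.1.3, 6.2.1 and 6.3.1, with a cross-reference in 6.2.4:

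- **Using NRT at the assessment:** verification by a friend or relative replaces cotinine. Identify NRT use from the daily NRT log and pharmacy refill data already planned in 6.1.3, and state the look-back period.
- **Not using NRT, with e-cigarette or smokeless use before but not within the window:** choose one route and state it in all three sections. Cotinine below 10 ng/mL is the suggested default. Use inside the window already fails self-report, and 7.5.1 describes the assay in these terms: "Laboratory studies will include salivary cotinine, a biomarker of recent tobacco use". Extending the 6.3.1 parenthesis to this group would also remove the contradiction, provided that the text says whether the contact replaces cotinine or is added to it.
- **Missing evidence:** score as non-abstinent only when it is missing on the route that applies to that participant.
- **Reporting:** show abstinence by verification route within arm.

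The cost is wording in three sections, a cross-reference and one extra table. The samples, contacts, log and refill data are already planned. The downside is that participants confirmed only by a contact have no biological confirmation, so fewer cases can be called bioverified.

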6.1.4 Intervention Administration

Intervention Condition: Participants will receive (1) eight 20- to 30-minute telephone sessions [initial session is aproximately 45-60 minutes]; and use (2) technology components (SQC app and iCO Smokerlyzer) between sessions. The therapist will proactively contact participants for each telephone session and use the accompanying workbook. At Week 0, participants will download the SQC app to their personal smartphones and be instructed to use SQC as much as desired between sessions. Participants will receive a brief training and orientation about features of SQC and will populate SQC with personalized information (planned guit date, triggers to smoke and coping plan, reasons to guit, and medications prescribed) in the weeks leading to the guit attempt (Week 5). At Week 0, participants will also receive an iCO Smokerlyzer mobile device for their personal use and will download the compatible Covita iCO app to their personal smartphones that displays CO readings. They will receive training on use of the iCO monitor and app and will be encouraged to measure CO levels as much as desired throughout the study period. Information will be stored on the apps on individuals' personal devices (no personal identifiers will be used and data will not be sent to or from participants, with anonymized data from the apps remaining on participants' phones).

Treatment Fidelity: Fidelity maintenance (1) ensures that the treatment delivered is the treatment intended, thereby safeguarding internal validity, (2) minimizes the influence of therapist effects, 80 and (3) facilitates dissemination and implementation by providing training programs and quality assurance procedures. Treatment fidelity ratings are a critical part of adherence to CONSORT guidelines as applied to psychosocial interventions. 81 Adherence to the treatment model, which is improved through fidelity maintenance procedures, is associated with improved outcomes in both research and clinical implementation. 82,83 The therapist will undergo a two-hour initial training with the PI, who is well-versed at delivering the original IC protocol. The therapist will then will attend a weekly supervision meeting with the PI. We will ensure a minimum of one hour of supervision per week for every four cases. Treatment sessions will be audiotaped using a telephone recording device that allows both sides of the conversation to be recorded. The PI will randomly select 10% percent of the audiotapes for adherence ratings by research clinical evaluators. This type of intensive

supervision will ensure therapist fidelity,⁸⁰ thereby minimizing threats of the internal validity of the study.

Control condition: Consistent with the current standard of care in VA clinics in rural areas, controls will be referred to the proactive VA Telephone QL. 55,84 Participants will receive instructions to call the VA QL 55,84 in Week 1 and will then request to receive weekly proactive telephone calls thereafter. They will be asked to track their weekly participation in QL sessions and duration of each session and will be instructed to request follow up calls weekly from the QL counselor for up to seven weeks thereafter (eight total). We selected the VA QL as a control because it accurately represents real-world treatment provided to veterans in VA settings, particularly in rural areas. The VA QL is a national toll-free number available to veterans that allows them to speak with a smoking cessation counselor for as many weekly sessions as needed (minimum recommended five sessions, more as needed) to develop a quit plan and receive counseling, strategies to prevent relapse, and weekly proactive follow-up calls based on National Cancer Institute guidelines. Sessions provide evidence-based smoking cessation counseling, but no resources or skills to manage mental health symptoms, such as PTSD symptoms, are provided.

